### **9.3. Patient confidentiality**

- In order to respect the privacy of the patient, in the form of the patient information record, the patient will be identified using the assigned patient number.
- The investigator will allow the monitor or auditor or sponsor-designated collaborator to access the patient's original medical records for verification of the data in the CRF. Patient confidentiality will be carried out in accordance with appropriate laws.

### **9.4. Modification and violation of the test protocol**

- The investigator will conduct the test according to the trial protocol after approval by the competent authority and ethics committee.
- The agreement will not be modified without the approval of the ethics committee and sponsor. All modifications to the protocol require prior approval by the ethics committee, except in cases where changes must be made to avoid immediate risk to the patient.
- Any violations of the scheme will be recorded in the CRF and the original records.

### **9.5. Early termination of the trial**

The study may be terminated early if the manufacturer, investigators or regulator of Ad-TD-nsIL12 deem it justified. If the trial is terminated prematurely, the sponsor should report the reason for the termination or suspension. Reasons for early termination or suspension of the trial include, but are not limited to:

- Patients present with serious risks not foreseen by the protocol.
- Unable to recruit a sufficient number of patients.
- Insufficient compliance with the protocol.
- Significant changes or pauses in drug development programs.

## **10. Statistical methods**

### **10.1. Study endpoints**

- Primary endpoint  
The maximum tolerated dose (MTD) of Ad-TD-nsIL12. (According to the criteria of NCI-CTCAE V5.0, MTD will be defined as doses below the dose that causes DLT. If no DLT has occurred at D3, the trial is terminated and MTD is not defined.)
- Secondary endpoints  
Tumor response based on tumor size change on continuous MRI scans after injection, time to progression, viral activity based on sample analysis, and immunogenicity based on adenovirus antibodies in serum. Overall survival of the patient. Due to the small number of participants, it is expected that the secondary endpoint will only be used to provide reference trends for future phase II efficacy studies.

### **10.2. Estimation of sample size**

Sample size was determined by the incidence of DLT in three dosing cohorts, each with 3 to 6 assessable participants. If DLT is not observed, at least nine participants will be included if MTD is not reached. Admission to nine participants was expected to take 10

to 12 months; 18 patients about 15-20 months.

### **10.3.Safety**

Patients who do not complete the study, for any reason, will include all available data prior to termination of the study in the safety analysis. AEs will be summarized by population and dose group, and tabulated by severity, relationship with Ad-TD-nsIL12, and causation. In addition, SAEs, AEs that may be related to Ad-TD-nsIL12, and AEs that are not related to Ad-TD-nsIL12 will be aggregated separately. Concurrent conditions will be listed and may be identified as possible confounding factors in the treatment-response relationship. Follow-up and treatment for AE will also be documented. Summary data includes univariate statistics for mean, standard error, percentage, and median. AE-related clinical laboratory results will provide descriptive statistics on selected laboratory parameters based on population, patients, study dates, and dose groups.

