- When the patient is discharged, the patient and his or her relatives will be provided with the investigator's contact information in case of an emergency. In addition,

after discharge, the patient can follow the recommended treatment of his/her pediatric oncologist in other hospitals, and the investigators of the experimental group will contact the hospital for follow-up visits. If the investigators think it is necessary, follow-up could be done at Sanbo Brain Hospital.

- Radiation therapy will start 2-6 weeks after the biopsy and virus injection at the discretion of the radiation therapist.

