#### 4.4. Follow-up period

- After enrollment, clinical follow-up will be conducted every 4 weeks for the first 3 months after viral treatment. After 3 months, follow-up visits can be performed by phone, images and blood tests results can be sent by email, or patients can come to our hospital for treatment and follow-up if they wish. Treatment tolerability was measured by severity classification of adverse events (NCI-CTCAE V5.0) and correlation with the investigating drug.
- Visit 1: 28±5 days after Ad-TD-nsIL12 injection. Including:
  - Physical examination, including vital signs, weight, and height.
  - Neurological examination and functional status assessment (LPS or KPS);
  - Quality of Life Assessment (PedsQL™);
  - Laboratory blood tests, some of which will be retained for subsequent analysis;
  - MRI (with or without gadolinium) and tumor response assessment;
  - Evaluation and documentation of adverse events, concomitant medications;
  - Steroid evaluation.
- Visit 2: 8±1 weeks after Ad-TD-nsIL12 injection. Including:
  - Physical examination, including vital signs, weight, and height.
  - Neurological examination and functional status assessment (LPS or KPS);
  - Quality of Life Assessment (PedsQL™);
  - Laboratory blood tests, some of which will be retained for subsequent analysis;
  - MRI (with or without gadolinium) and tumor response assessment;
  - Evaluation and documentation of adverse events, concomitant medications;
  - Steroid evaluation.
- Visit 3: 12±1 weeks after Ad-TD-nsIL12 injection. Including:
  - Physical examination, including vital signs, weight, and height.
  - Neurological examination and functional status assessment (LPS or KPS);
  - Quality of Life Assessment (PedsQL™);
  - Laboratory blood tests, some of which will be retained for subsequent analysis;
  - MRI (with or without gadolinium) and tumor response assessment;
  - Evaluation and documentation of adverse events, concomitant medications;
  - Steroid evaluation.
- Visit 3 is the last designated clinical follow-up, after which the patient's overall AE will be concluded and assessed.
- Except for the 3 planned visits, both patients and investigators may request unplanned follow-up at any time.
- During follow-up, if viral infection of CSF is suspected, the investigator will decide whether to perform virological (AdV) testing.

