**4.10. Duration of participation of each patient**

Each patient will receive viral injections prior to any other oncology treatment and will undergo clinical and radiological follow-up within 3 months after Ad-TD-nsIL12 treatment. Then, patients will continue to be followed up until two years. The research team will contact each patient by phone or mail at 6, 12, 18 and 24 months to update clinical information. Patients will continue to receive follow-up until five years if they are still alive at 24 months after viral treatment. At any time, patients can freely withdraw.

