## **8. Adverse event (AE)**

### **8.1. Document of adverse events**

All AEs will be recorded in a Case Report Form (CRF), either during clinical follow-up or voluntarily reported by the patient and their families, and graded according to NCI-CTCAE v5.0. If the investigator determines that a dose-related SAE (grade 3-4) has occurred, the safety committee will evaluate the AE and make changes to the admission of subsequent patients or even stop the recruitment of subsequent participants. AE is recorded until 12 weeks after viral injection as required by the protocol.

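### Section 10.3 summarises adverse events by dose without separating time before and after radiotherapy starts, so the 12-week descriptive safety summaries can mix virus and radiotherapy effects

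*Protocol*

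**What the plan says.** Section 1.1 makes safety, tolerability and toxicity the main objective. The primary endpoint in section 10.1 is narrower: the MTD.

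The virus comes first (section 4.10): "Each patient will receive viral injections prior to any other oncology treatment". Radiotherapy follows within weeks (section 4.3): "Radiation therapy will start 2-6 weeks after the biopsy and virus injection at the discretion of the radiation therapist".

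Adverse events are collected across both treatments. Section 8.1: "AE is recorded until 12 weeks after viral injection as required by the protocol". Section 4.4: "Visit 3 is the last designated clinical follow-up, after which the patient's overall AE will be concluded and assessed".

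For the analysis, section 10.3 states: "AEs will be summarized by population and dose group, and tabulated by severity, relationship with Ad-TD-nsIL12, and causation". It adds that "SAEs, AEs that may be related to Ad-TD-nsIL12, and AEs that are not related to Ad-TD-nsIL12 will be aggregated separately" and that "Concurrent conditions will be listed and may be identified as possible confounding factors in the treatment-response relationship". Radiotherapy is not named in section 10.3, and no division of follow-up time is given.

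The items listed for Visits 1 to 3 in section 4.4 include "Evaluation and documentation of adverse events, concomitant medications" and an evaluation of steroids. Neither that list nor the remote follow-up list in section 4.5 names radiotherapy dates.

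**The concern.** Every patient who follows the plan spends the first 2 to 6 weeks with virus and biopsy effects only, and the rest of the 12 weeks with radiotherapy added. A table by dose group over the whole span counts events from both periods together. A reader who wants the toxicity of the virus then depends on one judgement per event, made by the principal investigator in an open single-arm trial (sections 4.1 and 8.4).

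That judgement has a soft edge. Section 8.4 counts only its two highest causality levels as related, whereas section 10.3 groups events that may be related. An event rated possible, a natural rating once radiotherapy has begun, is unrelated under the first and arguably included under the second.

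Several primary assessments in section 6.1 (neurological examination, performance score, laboratory results, concomitant drugs) are given no causality rating at all. For these, only timing could tell the periods apart.

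**Working it through.** **The plan's own figure.** Sections 1.6 and 10.2 give 9 to 18 patients. Three cohorts of 3 give 3 × 3 = 9, and three cohorts of 6 give 3 × 6 = 18. The figure reproduces and the point below does not change it. The protocol states no alpha or power to check.

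**Inputs.** Adverse-event window: 12 weeks = 84 days (section 8.1). Radiotherapy start: day 14 to day 42 (section 4.3). Inclusion window within a cohort: 6 days; escalation window: 10 days (section 4.8).

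**Share of the window after radiotherapy start**, (84 − start day) / 84:

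| Start | Days before | Days after | Share after |
|---|---|---|---|
| Day 14 | 14 | 70 | 83% |
| Day 28 | 28 | 56 | 67% |
| Day 42 | 42 | 42 | 50% |

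The days after are all time from the first radiotherapy day, not days under treatment; the protocol gives no course length.

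**Scheduled visits.** Visit 0 (days 2 to 4) always precedes radiotherapy. Visit 1 (28 ± 5, so days 23 to 33) lies inside the start range, so some patients will have begun and others not. Visit 2 (8 ± 1 weeks, so days 49 to 63) follows every start within the range.

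**Possible imbalance between doses.** Two patients can differ by at most 70 − 42 = 28 days after start. Cohort means differ less. The protocol gives only the range, so I assume a start uniform over days 14 to 42 and unrelated to dose. In 200,000 simulated trials, the gap between the largest and smallest of the three cohort means had a median of 7.6 days (95th percentile 15.2) with 3 per cohort, and 5.3 days (95th percentile 10.8) with 6 per cohort.

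**What timing alone could do to one patient's risk.** This is an illustration with no virus effect and an assumed constant hazard after radiotherapy start. If the risk over 56 days is p, the risk over d days is 1 − (1 − p)^(d/56).

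| p over 56 days | Start week 2 (70 days) | Start week 6 (42 days) |
|---|---|---|
| 10% | 12% | 8% |
| 20% | 24% | 15% |
| 30% | 36% | 24% |

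**Dose escalation.** The earliest radiotherapy day is 14, and 14 − 10 = 4. The 10-day window closes at least 4 days before radiotherapy, and the 6-day window earlier still.

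**Rules without a window.** The section 4.8 rules that count one or two drug-related SAEs in a cohort give no period. At the minimum 6-day spacing, when the last patient completes 10 days the first is at day 2 × 6 + 10 = 22 (three patients) or 5 × 6 + 10 = 40 (six patients). Both lie within the radiotherapy start range. Read without a time limit, these rules could admit an event from after radiotherapy start if it were judged drug-related.

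**The case against.** The strongest objection is that dividing adverse-event tables by period is layout, which a protocol may leave to an SAP that is not shown. Section 10.3 does not forbid a split, and it names no period at all. This stands for the table alone. It does not cover data collection: an SAP can split only on dates that are recorded, and the listed visit items do not include them.

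Second, section 10.3 already separates events by relationship and causation, lists concurrent conditions as possible confounders, and describes event-related laboratory results by study date. That reduces the mixing but does not remove it, because radiotherapy is not named and the classification rests on judgement.

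Third, a reader might infer that the split could never be made later. The documents do not support that. The CRF is not shown, section 4.3 has the investigators contact outside hospitals for follow-up, and section 9.3 gives access to original records. The dates may be recoverable; the plan just does not schedule them.

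Fourth, the protocol lists no radiotherapy toxicities, so overlap between the two treatments' adverse effects is an assumption, though a modest one. After a split, the later period would still combine virus, radiotherapy and disease effects. Only the earlier period becomes cleaner.

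**Conclusion.** This is a worthwhile, inexpensive improvement to the descriptive safety analysis, not an error in the primary endpoint's design. Its size is arithmetic: 50% to 83% of each patient's 84-day window falls after radiotherapy start, provided radiotherapy begins in the stated range and the patient is followed to week 12. Mixing occurs within every dose group and needs no imbalance between them.

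Two stronger readings are tempting and unsupported. One is that the tables mix toxicity unequally across doses. No text ties radiotherapy timing to dose. The largest contrast (70 against 42 days, 1.67-fold) would need every patient in one cohort to start at week 2 and every patient in another at week 6; under random timing, the median gap between extreme cohort means is about 5 to 8 days. The other is that radiotherapy contaminates escalation and the MTD. The stated 6-day and 10-day windows both close before day 14. What remains is that the SAE-counting rules beside them have no stated window, which is a separate inconsistency.

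**What to change.** 1. Add radiotherapy start and stop dates to the items recorded at Visits 1 to 3 in section 4.4 and to the CRF.
2. In section 10.3, keep the overall table. Beside it, report adverse events by dose group for (a) injection to the day before radiotherapy and (b) radiotherapy start to week 12, each with patient-days. Patients who do not start radiotherapy contribute only to (a).
3. Reconcile the rules in section 4.8: those that count one or two drug-related SAEs state no period, while the neighbouring rules use 6 and 10 days. Which period applies is for the investigators and sponsor to decide.

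The cost is two date fields and one more table layout. No new visit, patient or outcome is needed. The downside is sparser tables: with 3 to 6 patients per dose, many cells will hold no events or one, so the split should be read descriptively.

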#### **4.6. Follow-up of laboratory tests**

Basic blood tests will be done before and early (within 3 days) after virus injection, and during 1 to 3 visits. These tests will include, but are not limited to:

- Hematology: white blood cell count with differential, including neutrophils, lymphocytes, monocytes, eosinophils and basophils, red blood cell count, hemoglobin, hematocrit, platelets, mean platelet volume (MPV), MCV, MCH, MCHC, RDW.
- Chemical and C-reactive proteins: glucose (fasting), creatinine, sodium, potassium, chloride, calcium and C-reactive proteins.
- Coagulation: PT, APTT

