# **6. Response assessment**

## **6.1. Primary assessment**

- Adverse events (according to NCI-CTCAE v 5.0)
- Neurological examination
- LPS or KPS score
- Laboratory test results
- Use of concomitant drugs

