### **8.3. Definition of adverse events**

Refer to the occurrence or worsening of any adverse medical event (e.g., signs, symptoms, disease, syndrome, intercurrent illness, abnormal laboratory findings) relative to baseline levels following the administration of an intervention (pharmacotherapy). AE is not necessarily causally related to drug use. Therefore, AE can be any adverse and/or unexpected sign (including abnormal laboratory results), symptoms, and diseases that are not associated with drug use. Common events/symptoms during surgery (e.g., pain, headache, changes in standard blood pressure, constipation, etc.) are usually within the normal range. Long-term, latent, disease-related conditions that have not changed from baseline are not considered AEs. Exacerbations of underlying chronic conditions will be assessed for their "severity" and, if determined to be "severe," will be reported as SAE at the appropriate location on the form. SAE includes the following:

- Fatal
- Life-threatening

- Request or extend hospital stay
- Disability
- Can cause congenital anomalies/birth defects

In addition, any significant medical event can and should be reported to the sponsor as a SAE if deemed necessary by the principal investigator.

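### Section 10.3 limits the planned laboratory summary to AE-related results on selected parameters and names no SD or range; a minor safety-reporting point that is cheap to fix

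*Protocol*

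**What the plan says.** Four parts of the protocol bear on this.

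- **Status.** Section 6.1 (Primary assessment) lists "Laboratory test results" as an item of its own, separate from adverse events and without qualification. The primary endpoint in section 10.1 is a different thing: "The maximum tolerated dose (MTD) of Ad-TD-nsIL12".
- **Collection.** Section 4.6: "Basic blood tests will be done before and early (within 3 days) after virus injection, and during 1 to 3 visits". Hematology, chemistry with C-reactive protein, and coagulation are named, and the list is open-ended ("These tests will include, but are not limited to").
- **Analysis.** Section 10.3: "AE-related clinical laboratory results will provide descriptive statistics on selected laboratory parameters", with the sentence ending "based on population, patients, study dates, and dose groups". The general sentence before it, which covers safety data as a whole, reads "Summary data includes univariate statistics for mean, standard error, percentage, and median".
- **Link to adverse events.** Section 8.3 counts new or worsened abnormal laboratory findings as adverse events whatever the cause: "AE can be any adverse and/or unexpected sign (including abnormal laboratory results". Section 8.1 has all adverse events recorded and graded by CTCAE v5.0, and section 10.3 tabulates them by dose group, severity and relationship.

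**The concern.** The main objective is safety, tolerability and toxicity. Laboratory results are collected from everyone on a fixed schedule and called a primary assessment, but the one sentence on their analysis passes them through two filters: a link to an adverse event, and selection of the parameter. Neither has a rule. Once the summary depends on adverse event status, what is shown depends partly on judgement. That judgement is hardest just after surgery, because the virus is given immediately after the biopsy and section 8.3 treats common perioperative findings as usually normal.

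Lower-grade laboratory trends over the three doses are at stake. Escalation under section 4.8 responds to drug-related SAEs of grade 3 or higher, and section 8.4 counts only likely or certain relationships as related. A milder drift in, say, platelets or C-reactive protein from one dose to the next would therefore show up only in descriptive tables, and those need all 3 to 6 patients of each cohort.

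The second issue is the choice of statistics. With 3 to 6 patients, a safety reader wants to know how far patients differ and what the extreme value was. The list in section 10.3 names neither the SD nor the range.

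**Working it through.** **What is collected against what is planned for summary**

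| | Sections 4.6 and 6.1 | Section 10.3 |
|---|---|---|
| Patients | all | grouped by population, patient, date and dose group; denominator not stated |
| Parameters | full panel, open-ended | selected, no rule |
| Condition | none | AE-related |
| Time points | 1 before injection, 4 after | study dates |

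Named analytes in section 4.6:

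- Hematology: white cell count and 5 differential counts (6), plus red cells, hemoglobin, hematocrit, platelets, MPV, MCV, MCH, MCHC and RDW (9) = 15.
- Chemistry and C-reactive protein: glucose, creatinine, sodium, potassium, chloride, calcium, CRP = 7.
- Coagulation: PT, APTT = 2.
- Total 15 + 7 + 2 = 24, each at 1 + 4 = 5 time points.

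**What the adverse event route recovers**

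A new or worsened abnormal value meets the section 8.3 definition, is graded under section 8.1, and reaches the by-dose tables in section 10.3. Two things do not come through that route: changes not judged adverse, including shifts within normal limits; and values over time by dose, because adverse event tables hold counts by severity rather than measurements.

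**Standard error against SD**

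The protocol's sample size comes first, since it fixes n. Three cohorts of 3 to 6 give 3 × 3 = 9 and 3 × 6 = 18, which reproduces the stated 9-18.

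SE = SD/√n, so SE/SD = 1/√n and SD/SE = √n. For normally distributed values, with the true mean and SD, the share of patients within mean ± 1 SE is 2Φ(1/√n) − 1.

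| n | SE/SD | SD/SE | Share within mean ± 1 SE |
|---|---|---|---|
| 3 (smallest cohort) | 0.577 | 1.73 | 44% |
| 6 (largest cohort) | 0.408 | 2.45 | 32% |
| 9 (smallest total) | 0.333 | 3.00 | 26% |
| 18 (largest total) | 0.236 | 4.24 | 19% |

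Mean ± 1 SD would cover about 68% in every row. The ratio also depends on n, so equal standard errors in a cohort of 3 and a cohort of 6 stand for different spreads.

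**What can be recovered from the listed statistics**

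SD = SE × √n whenever n is shown. At n=3 the mean, median and standard error together even fix the three values: the middle value is the median, and the sum and the sum of squares of the other two follow. From n=4 upward there are more unknown values than equations, so the minimum and maximum cannot be recovered from these statistics alone.

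**The case against.** The case on the other side has several parts.

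- **Other laboratory summaries are not excluded.** True. *AE-related* may be loose wording for safety laboratory data in general. A reader might infer that most of the 24 analytes will never be summarised, but the protocol does not say so.
- **No denominator is stated.** True. A reader might infer that only patients with a flagged event enter the table. Section 10.3 does not say that. It groups results by population and dose group, and it brings all available data from non-completers into the safety analysis. Equally possible is that parameters relevant to adverse events are chosen and then summarised in everyone.
- **Nothing shows that selection follows sight of the data.** True. The timing is not given, and a parameter list may properly sit in a SAP.
- **By-patient presentation is already named.** True. In cohorts of this size it may show the extreme patient, so the documents do not support a claim that outliers are hidden. An outlier also inflates the standard error.
- **The standard error is not called a measure of spread.** True. The sentence is general, also names the median, and understates spread only if a reader takes it as spread.
- **The rest is SAP detail.** This stands only in part. Table layouts can wait for a SAP. A stated restriction to AE-related results is different: it is text already fixed, and a SAP that summarised everything would depart from it.

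**Conclusion.** The point holds as a minor one. The wording of section 10.3 is narrower than sections 6.1 and 4.6 call for, and it permits selective laboratory reporting; it does not establish that reporting will be selective. New or worsened abnormal values are covered by the adverse event tables. The possible loss is limited to changes not judged adverse and to dose trends across all treated patients.

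Within a cohort, the standard error is 1.7 (n=3) to 2.4 (n=6) times smaller than the SD. That is arithmetic and needs no distributional assumption; the coverage percentages assume normal values. It matters only where the standard error is read as between-patient variation.

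A reader might infer from the words *primary assessment* that the trial's primary result is at risk. It is not. The primary endpoint is the MTD, which rests on drug-related SAEs of grade 3 or higher and uses none of these summaries. The conclusion assumes that no other document already requires full laboratory tables.

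**What to change.** In section 10.3:

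1. Delete *AE-related* and *selected*. State that all scheduled laboratory parameters are summarised in all dosed patients, by dose group and visit, regardless of adverse event status.
2. Add a shift table from baseline to worst post-injection CTCAE grade, by dose group, for parameters that have a grade.
3. For continuous safety data, report n, median, SD, minimum and maximum in place of the standard error. The mean can stay.
4. Keep the by-patient presentation that the section already names.

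The cost is a change of wording and a few more tables. Section 4.6 already collects the data, so no visit, sample or patient is added, and the escalation rules and the MTD definition are untouched.
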